**Study Protocol and Study Analysis Plan**

## **Study Protocol**

### *Recruitment*

Patients from neurological and orthopedic surgery groups were recruited for the study at a 281-bed academic Medical Center in the greater Los Angeles area. Per approval by the University of California, Los Angeles, Office for Human Research Protection Program, research staff identified scheduled participants for surgery in the prone position, sent them an information sheet about the study, and then contacted them by phone to determine their interest in the study. Participants were eligible for the study if they were scheduled to undergo orthopedic or neurological surgery in prone position, 18 years of age or older, and able to provide verbal informed self-consent. Exclusion criteria were less than 18 years old, inability to provide verbal informed consent, and scheduled for surgery only in a position other than prone position.

### *Skin Assessments*

On the day of surgery, research staff obtained written HIPAA consent from participants and confirmed consent to participate in the study. Research staff collected visual skin assessment and sub-epidermal (SEM) measures for all participants at the anterior chin, upper cheeks, mid forehead (face), right and left upper chest above nipple line, and iliac crest, both pre-operatively in the Pre-Post Anesthesia Care Unit (PACU) and post-operatively in the PACU or after transfer to the floor unit. Once the pre-operative assessments were completed for intervention participants, research staff placed the multidimensionally flexible silicone foam (MFSF) dressings to the face (chin, cheeks, forehead), chest and iliac crest. Following surgery, research staff removed the MFSF dressings in the PACU or on transfer to the floor unit and then visual skin assessment and SEM measures were obtained. For all participants, visual skin assessments

and SEM measures were obtained daily on the floor unit until post-operative day five or discharge from hospital (whichever occurred first).

*Visual Skin Assessment.* Trained research staff assessed skin health through direct independent visual assessments. Eight anatomic locations were assessed: mid forehead, chin, and right and left upper cheek, upper chest above nipple line and iliac crest. Areas of visual skin discoloration were palpated for blanchability in persons with light skin tones and any pressure injuries (PrIs) were assessed for size and stage. Training for visual skin assessment emphasized identification of stage 1 PrIs and deep tissue injury (DTI) because these conditions may be difficult to detect. Skin discoloration severity was graded as slight (pink or slight redness in persons with light skin tones and increase in normal skin color in persons with dark skin tones), minimal (redness in persons with light skin tones and deepening of normal skin color in persons with dark skin tones), moderate (bright redness in light skin tones and purple in dark skin tones), or severe discoloration (dark red to purple in light skin tones and black to blue-grey in dark skin tones). In persons with light skin tones, blanchability based on finger palpation was defined as blanchable or non-blanchable; blanching was not considered for persons with dark skin tones. Stage 1 PrIs were defined as skin discoloration with severity of minimal or greater. PrIs more severe than Stage 1 were classified using the NPIAP's 2019 classification system. For skin that demonstrated none of the above visual characteristics, the assessment was considered normal skin. The presence or absence of scar tissue, dry skin, rashes, skin tears, tattoos, and extensive or thick hair was also recorded.

*Subepidermal Moisture Measures.* Subepidermal moisture (SEM) was measured at each anatomic location on clean dry skin using the Provizio ® SEM Scanner (BBI LLC, Bruin Biometrics, Los Angeles, California, US) dermal phase meter. Using dielectric parameters, the

device transmits high-frequency, low-power electromagnetic waves of 32 kHz via an electrode that requires light skin touch. In the skin, the induced electrical field interacts mainly with water molecules closest to the electrode, with depth of interaction depending on the diameter of the circular electrode (in this study depth was 4 mm). The portion of electromagnetic energy that is not absorbed by tissue water is reflected and measured by the device and displayed in three seconds in the measuring unit picoFarads (pF) (range, 0-7 pF). The electrical properties of free and bound water are nearly identical and thus the measure is reflective of total water content in the tissue.

*Definition Intraoperative Acquired PrIs.* Intraoperative acquired PrI (IAPrI) was defined two ways for each anatomic location. First, as erythema/skin discoloration of minimal or greater severity by visual skin assessment. Second, by calculating the difference between pre-operative and the post-operative SEM value (hereafter SEM Delta); SEM Deltas greater than or equal to 0.6pF were considered indicative of IAPrIs.

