### **Study Analysis Plan**

The two outcome measures, IAPrI incidence by visual assessment and SEM Deltas indicative of PrI, were compared between participants undergoing prone surgery with standard care (no dressings, pressure reduction positioning on the operating table) and those with standard care and the intervention (use of MFSF dressings placed on chest, iliac crest, and face). Using Fisher's Exact test statistics, the percent of participants with IAPrI on face, chest, and iliac crest as defined above were compared between the two groups for initial post-operative assessment and postoperative days 2 and 3 assessments. There were insufficient participants to evaluate postoperative days 4 and 5.

Using binary logistic regression analyses, demographic, medical and surgical factors were compared for prospective participants who did and did not develop skin damage or IAPrIs controlling for group. Factors that increase risk for IAPrIs were evaluated including: hospital length of stay, surgery length, body mass index (BMI), and skin tone. Cochran Mantel-Haenszel statistics were used to compare the groups.

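### No allocation method is described, and the dressing comparison is an unadjusted Fisher's exact test, so it is open to case-mix bias

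*Combined protocol and SAP*

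**What the plan says.** The Recruitment section says that staff found eligible patients from scheduled prone operations, then "sent them an information sheet about the study, and then contacted them by phone to determine their interest in the study". On the day of surgery, under Skin Assessments, "research staff obtained written HIPAA consent from participants and confirmed consent to participate in the study". The same section continues: "Research staff collected visual skin assessment and sub-epidermal (SEM) measures for all participants", before and after the operation. Dressings come next: "Once the pre-operative assessments were completed for intervention participants, research staff placed the multidimensionally flexible silicone foam (MFSF) dressings to the face". After the operation the same staff role takes them off: "Following surgery, research staff removed the MFSF dressings in the PACU or on transfer to the floor unit and then visual skin assessment" and SEM readings follow.

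Of the visual grading, the section says only: "Trained research staff assessed skin health through direct independent visual assessments". It does not say that assessors were unaware of group.

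The second outcome, SEM Delta, is formed from the pre-operative and post-operative readings and cut at 0.6 pF. The visual outcome is a severity grade with no baseline subtracted.

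Under Study Analysis Plan, the two outcomes were "compared between participants undergoing prone surgery with standard care (no dressings, pressure reduction positioning on the operating table") and those given dressings as well, using Fisher's exact test. A logistic regression then examines factors associated with skin damage while controlling for group. A final sentence mentions Cochran-Mantel-Haenszel statistics without naming strata.

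**The concern.** An unadjusted comparison of two groups can be read as a dressing effect only if the groups are otherwise alike, or if chance alone made them differ. Nothing in the text secures either. Followed as written, a site could decide the group by surgical service, calendar period or staff availability. Staff working from the surgical schedule may have known the service, and perhaps the expected length, beforehand.

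The plan itself treats such features as important. Surgery length, BMI and skin tone are listed as risk factors to evaluate, and the Scott-Triggers score gives a point for an estimated surgery time over 3 hours. Patients also come from two services, neurological and orthopedic.

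A second, conditional issue concerns SEM Delta. If the person taking the pre-operative reading knew the group, one of the two numbers forming that outcome was open to influence. Masking the post-operative assessor would not repair this.

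**Working it through.** The documents give no sample size, event rate, SEM standard deviation, alpha or allocation ratio, so there is no planned figure to reproduce. The check is a reading of the text, followed by illustrations on assumed inputs.

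**1. Search for an allocation step.** The described order is: schedule, information sheet, phone call, day-of-surgery consent, pre-operative readings, dressings. No step gives a random sequence, concealment, a ratio, a matching rule, a time of assignment or the person responsible.

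**2. Search for adjustment.** Fisher's tests use no covariates. The regression contrasts participants with and without skin damage and includes group as a control; it is not presented as an adjusted estimate of the dressing effect. The Cochran-Mantel-Haenszel analysis could adjust, but its strata are not stated.

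**3. Size of a case-mix effect (assumed risks, no true dressing effect).** If a fraction f of an arm has the risk factor, its event rate is f × r1 + (1 − f) × r0.

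With r1 = 40% and r0 = 15%:
- 60/40 imbalance: 0.6 × 0.40 + 0.4 × 0.15 = 30%, against 0.4 × 0.40 + 0.6 × 0.15 = 25%. Difference: 5 points.
- 70/30 imbalance: 0.7 × 0.40 + 0.3 × 0.15 = 32.5%, against 0.3 × 0.40 + 0.7 × 0.15 = 22.5%. Difference: 10 points.

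With a wider assumed contrast, r1 = 40% and r0 = 10%, the chance that a two-sided Fisher's test at an assumed 0.05 rejects was found by exact enumeration:

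| Share with risk factor, by arm | Event rates | 25 per arm | 50 per arm | 100 per arm |
|---|---|---|---|---|
| 50% / 50% | 25% v 25% | 2.2% | 3.0% | 3.4% |
| 40% / 60% | 22% v 28% | 3.8% | 7.2% | 12.7% |
| 30% / 70% | 19% v 31% | 9.2% | 21.7% | 43.8% |

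**4. What stratification would do.** In the first example, both arms have a 40% risk among long operations and 15% among shorter ones. The within-stratum differences are 40 − 40 = 0 and 15 − 15 = 0, so a comparison stratified on operation length removes the spurious 5 or 10 points. The bias comes from the unadjusted comparison and can be corrected for recorded factors, though not for unrecorded ones.

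**5. Size of a baseline-reading effect on SEM Delta (assumed).** Take Delta as post-operative minus pre-operative, normal with mean 0.2 and SD 0.4 pF. Then P(Delta ≥ 0.6) = 1 − Φ((0.6 − 0.2 + b)/0.4), where b is the amount by which baseline is read too high in one arm.
- b = 0: 1 − Φ(1.00) = 15.9%
- b = 0.1 pF: 1 − Φ(1.25) = 10.6%
- b = 0.2 pF: 1 − Φ(1.50) = 6.7%

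Over means of 0 to 0.2 and SDs of 0.3 to 0.6 pF, a shift of 0.2 pF moves the range of rates from 2.3%–25.2% to 0.4%–15.9%. With one site per participant, mean 0.2 and SD 0.4, Fisher's test at 25, 50 and 100 per arm rejects in 3.3%, 6.6% and 14.9% of trials for a 0.1 pF shift, and in 6.6%, 18.8% and 46.2% for 0.2 pF.

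**The case against.** The strongest reply is that silence is not absence. The text is a short account written after the event, and part of the file was not available here, so an allocation procedure may have existed. This is fair: the text does not show that assignment was non-random. What stands is that no procedure is described, and the analysis as written does not protect against the alternative.

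Several stronger readings are tempting but not supported:

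- **That group was fixed and known before baseline.** Calling people intervention participants at that point may only label, in hindsight, those who later received dressings. Allocation between baseline and dressing placement fits the same sentence. Even then, without concealment, assignment could follow the baseline skin findings.
- **That baseline SEM was biased.** This also requires staff to have known the group, which is not stated. SEM is a displayed device value, which limits discretion (though not over exact site or repeat readings). The visual outcome does not use this baseline.
- **That patients dropped out because they knew their arm.** Nothing says the arm was disclosed at the phone call.
- **That case mix could not be told apart from a dressing effect.** Surgery length and type are among the data abstracted from the records, and surgery length is named in a regression that includes group. Adjustment is feasible; it is simply not specified for the dressing effect.

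It is also true that the plan never calls the study randomised and states no causal conclusion.

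**Conclusion.** The point holds in a limited form. The text describes no random or concealed allocation and does not say when or by whom group was assigned, while the dressing comparison rests on unadjusted Fisher's tests. That leaves both outcomes open to case-mix bias. Exposure of the baseline within SEM Delta is conditional on group having been known at the pre-operative reading.

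The size cannot be determined from the documents. The 5- and 10-point differences, the rejection rates and the SEM shifts all rest on assumed risks, imbalances, distributions and sample sizes; they show what is possible, not what happened. The conclusion is that the comparison is open to bias, not that it is biased, and it covers only the Study Protocol and Study Analysis Plan text reviewed.

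**What to change.** **Participants already enrolled.** The past tense, and the remark that too few participants remained to evaluate days 4 and 5, suggest that enrolment is finished, so this is the main repair. State under Skin Assessments and Study Analysis Plan how, when and by whom group was assigned. If assignment was not random:

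- Make the main dressing comparison confounder-adjusted, with group as the effect of interest, by Cochran-Mantel-Haenszel with named strata or by logistic regression. Use data already collected, for example surgery type or service, surgery length, BMI and Scott-Triggers score.
- Keep the set small if events are few. The Scott-Triggers score already contains BMI and estimated surgery time, so it overlaps with those factors. Hospital length of stay follows the dressing and should not be an adjustment variable for its effect.
- Report Fisher's test as the unadjusted result, and limit the conclusion to association.

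The cost is a few sentences, a reanalysis of existing data, some loss of precision and a weaker stated conclusion. Unmeasured confounding remains.

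**Any further enrolment.** Allocate from a concealed computer-generated list stratified by surgical service. Open it only after consent is confirmed and the pre-operative skin and SEM values are entered, and analyse participants in the assigned arm. The cost is a list, a concealment method such as numbered opaque envelopes or the study database, and a dressing set on hand for every participant.

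### The visual IAPrI outcome counts blanching and non-blanching discoloration alike, so the between-arm comparison can be biased in either direction; a labelled sensitivity analysis would show whether this matters

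*Combined protocol and SAP*

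**What the plan says.** Under Skin Assessments, the Visual Skin Assessment paragraph describes a palpation step: "Areas of visual skin discoloration were palpated for blanchability in persons with light skin tones". The result has two categories in light skin tones ("blanchability based on finger palpation was defined as blanchable or non-blanchable"), while "blanching was not considered for persons with dark skin tones".

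The same paragraph grades color in four steps. The lowest is "slight (pink or slight redness in persons with light skin tones", with a matching description for dark skin. The next is "minimal (redness in persons with light skin tones and deepening of normal skin color in persons with dark skin tones". The injury rule starts at that second step: "Stage 1 PrIs were defined as skin discoloration with severity of minimal or greater". An external staging system enters only above that level: "PrIs more severe than Stage 1 were classified using the NPIAP's 2019 classification system".

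The paragraph defining intraoperative acquired injuries repeats the threshold for the first of two outcomes: "erythema/skin discoloration of minimal or greater severity by visual skin assessment". The second outcome is a pre-to-post change in subepidermal moisture (SEM Delta) of at least 0.6 pF.

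The Study Analysis Plan compares both outcomes between arms with Fisher's exact test at the initial post-operative assessment and on days 2 and 3. It lists skin tone among the risk factors and names Cochran Mantel-Haenszel (CMH) statistics. It does not mention blanchability.

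**The concern.** The trial assessed a property of the discoloration and then left it out of the outcome definition, the tests and any sensitivity analysis. In light skin tones, redness that blanches and redness that does not are scored as the same event.

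Two things are at stake. The visual incidence may include blanching redness as well as whatever non-blanching injury occurred. The comparison of arms may also partly reflect how the dressing affects redness rather than how it affects injury. The initial post-operative reading is the most exposed. It is the closest to the period of pressure, and in the intervention arm it comes after the dressing has been taken off. It is one of only three analysed time points.

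**Working it through.** **Tracing the item through the documents**

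| Place | Is blanchability used? |
|---|---|
| Visual Skin Assessment, palpation step | Assessed, light skin tones only |
| Visual Skin Assessment, Stage 1 rule | No, color severity alone |
| Definition of intraoperative acquired injury, visual | No, color severity alone |
| Definition of intraoperative acquired injury, SEM Delta | Not applicable |
| Study Analysis Plan | No |

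No later rule restores the distinction, because the external staging system applies only above Stage 1.

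**What this could do to the comparison**

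The plan states no sample size, event rate, effect size or alpha, so there is no figure of its own to reproduce. All inputs below are assumptions.

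- p = true rate of injury in an arm. Two pairs are tried, control vs dressing: 20% vs 5% and 20% vs 10%.
- f = chance that a participant without injury shows blanching discoloration graded minimal or worse, from 0 to 30%.
- Test: Fisher's exact, two-sided 0.05, equal arms of 50 or 100, by full enumeration.

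Observed rate = p + (1 − p) × f.

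Example, 20% vs 5% with f = 10% in both arms: control 0.20 + 0.80 × 0.10 = 0.28; dressing 0.05 + 0.95 × 0.10 = 0.145; risk ratio 0.145 / 0.28 = 0.52.

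True rates 20% vs 5% (true difference 15 points, true risk ratio 0.25):

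| f control / f dressing | Observed rates | Difference (points) | Risk ratio | Power, 50 per arm | Power, 100 per arm |
|---|---|---|---|---|---|
| 0 / 0 | 20% vs 5% | 15 | 0.25 | 51% | 88% |
| 10% / 10% | 28% vs 14.5% | 13.5 | 0.52 | 30% | 59% |
| 20% / 20% | 36% vs 24% | 12 | 0.67 | 20% | 40% |
| 30% / 30% | 44% vs 33.5% | 10.5 | 0.76 | 14% | 28% |
| 20% / 10% | 36% vs 14.5% | 21.5 | 0.40 | 64% | 93% |
| 30% / 5% | 44% vs 9.75% | 34.25 | 0.22 | 97% | over 99% |
| 10% / 20% | 28% vs 24% | 4 | 0.86 | 5% | 7% |

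True rates 20% vs 10% (true difference 10 points, true risk ratio 0.50):

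| f control / f dressing | Observed rates | Difference (points) | Risk ratio |
|---|---|---|---|
| 10% / 10% | 28% vs 19% | 9 | 0.68 |
| 30% / 30% | 44% vs 37% | 7 | 0.84 |
| 20% / 10% | 36% vs 19% | 17 | 0.53 |
| 30% / 5% | 44% vs 14.5% | 29.5 | 0.33 |
| 10% / 20% | 28% vs 28% | 0 | 1.00 |

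**Reading the tables**

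- Equal f in both arms: the difference shrinks by the factor (1 − f), the risk ratio moves toward 1 and power falls.
- Dressing lowers redness: the difference and the power grow beyond what injury alone would give. The risk ratio can land on either side of the truth (0.40 or 0.22 against 0.25).
- Wearing or removing the dressing adds redness: a real effect can be nearly or wholly hidden.

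**How much the item could correct**

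Only light skin tones were classed, so a rule using blanchability can remove false positives only there. The documents do not give that share. If it were 70% (assumed), with blanching redness counted only in that group, f averages 7% to 21% over the arm. At 20% vs 5% the risk ratios become (0.05 + 0.95 × 0.07) / (0.20 + 0.80 × 0.07) = 0.1165 / 0.256 = 0.46 and (0.05 + 0.95 × 0.21) / (0.20 + 0.80 × 0.21) = 0.2495 / 0.368 = 0.68.

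**The case against.** A reader might infer that blanching redness must dilute any effect of the dressing. The documents do not support this. Dilution requires redness to be equally frequent in both arms, and the dressing covers the assessed sites during surgery and is removed before the first reading. As the tables show, unequal redness can push the result either way. The word any is also too wide, because SEM Delta does not depend on blanching.

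Other points on the plan's side:

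- Slight discoloration is already below the threshold, so faint pinkness is not counted. This stands.
- Days 2 and 3 are analysed too, and redness that fades has time to do so. This stands, and it confines the concern mainly to the initial reading.
- One severity rule for all skin tones is a defensible choice. A stricter rule in light skin only would build a difference in ascertainment into the skin-tone risk-factor analysis. This stands as a reason to keep the present definition as the main one. It does not argue against a second, labelled analysis.
- The documents nowhere say that blanching separates passing redness from injury, and palpation may misclassify. This stands, so the second analysis tests robustness and does not supply a corrected truth.
- It is not stated outright that the palpation result was recorded. The two-category definition makes this likely, but it needs checking.
- The plan is written in the past tense and reports that too few participants remained to analyse days 4 and 5. A new definition can hardly be called pre-specified now. Making the conclusion conditional on it would replace the stated outcome with one that has fewer events. This stands.

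**Conclusion.** The point holds in a limited form. The visual outcome mixes blanching with non-blanching discoloration in light skin tones, although the trial assessed the difference. Visual incidence may therefore include blanching redness, and the comparison between arms may be biased in a direction the documents do not settle.

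Under the assumed rates, the observed risk difference ranges from 4 to 34 points against a true 15, and from 0 to 29.5 points against a true 10. These figures show that the bias could matter, not that it did. They rest on assumed injury rates, redness rates and arm sizes, and on perfect palpation.

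This is a cheap improvement to interpretation. It does not invalidate the visual outcome, and it leaves the SEM Delta outcome untouched.

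**What to change.** Keep the severity definition as the main visual outcome. Add to the Study Analysis Plan:

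1. A sensitivity analysis of visual IAPrI in which discoloration graded minimal or worse counts in light skin tones only if non-blanchable. The severity rule stays unchanged in dark skin tones.
2. A comparison of arms under this definition, stratified by skin tone with the CMH test already named, at the same three time points. Report it side by side with the main result.
3. A label: post hoc if outcomes have been seen when it is added.
4. A statement that this definition is not used for the skin-tone risk-factor comparison.
5. A rule for wording: if the two results differ, the conclusion refers to an effect on discoloration, not on pressure injury.

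The cost is a few lines of text and one extra set of tables, with no new measurements. The drawbacks are fewer events, a definition that differs by skin tone, and dependence on the palpation result having been recorded. If it was not recorded, state that as a limitation of the visual outcome.

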#### *Medical Record Data*

Research staff extracted medical, surgical, and demographic information was extracted from participants' electronic health records (EHR) using an investigator-developed abstraction tool. Data abstracted included demographic data (gender, age, race/ethnicity), medical data (height, weight, body mass index, comorbidities such as diabetes, hypertension, peripheral vascular disease and, smoking status, medical diagnoses, Braden Scale for predicting Pressure Sores (Braden) score, use of any PrI preventive strategies such as support surface use, repositioning schedules), surgery type, surgery length, use of vibration machines or other instruments in surgery, length of time in PAR unit, anesthesia used, use of vasopressors during surgery, estimated blood loss, volume of fluids provided during surgery, blood pressure during

surgery, American Society of Anesthesiologists physical status score and documentation of any skin damage. Using EHR data, a Scott-Triggers IAPrI risk assessment score was calculated for each participant. The Scott-Triggers tool examines four characteristics: age 62 years or older; albumin less than 3.5mg/dL or BMI less than 19 or greater than 40; American Society of Anesthesiologists physical status classification system (ASA) 3 or greater; and estimated surgery time over 3 hours. Each characteristic affirmed scores a point and scores greater than 1 indicate high risk for IAPrIs (37).

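### The SEM definition of intraoperative pressure injury cannot separate local pressure damage from a general or positional fluid shift, and no fluid-adjusted comparison of the arms is specified

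*Combined protocol and SAP*

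**What the plan says.** Under Skin Assessments, the protocol states that the scanner does not distinguish free from bound water: "thus the measure is reflective of total water content in the tissue". The reading depth is given ("in this study depth was 4 mm") and the scale runs from 0 to 7 pF.

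Intraoperative acquired pressure injury (IAPrI) is then defined in two ways at each location. One is visual: discoloration of at least minimal severity. The other is obtained "by calculating the difference between pre-operative and the post-operative SEM value (hereafter SEM Delta"), with the rule that "SEM Deltas greater than or equal to 0.6pF were considered indicative of IAPrIs". The sign of the subtraction is not stated; a rise from before to after surgery is the natural reading.

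The eight locations are the forehead, the chin, and the right and left cheek, upper chest and iliac crest. None is designated as a reference.

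Medical Record Data lists "volume of fluids provided during surgery" among the abstracted items, along with blood loss and surgery length.

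The Study Analysis Plan names visual IAPrI and SEM Delta as the two outcome measures. It compares the arms by Fisher's exact test at the first post-operative assessment and on days 2 and 3. It also describes logistic regression of demographic, medical and surgical factors, controlling for group: "Factors that increase risk for IAPrIs were evaluated including: hospital length of stay, surgery length, body mass index (BMI), and skin tone". A last sentence says that Cochran-Mantel-Haenszel statistics were used to compare the groups, without naming strata.

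**The concern.** Between the two readings a participant may receive intravenous fluid and lies face-down. Either could raise tissue water at the measured sites without local pressure damage. A device that reads total water cannot tell the two apart. The definition does not help either: it compares a site only with itself over time, subtracts no shift common to all sites, and does not require the visual finding to agree.

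Two things are at stake for the SEM outcome.

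- **Specificity.** False positives that are equally common in both arms dilute any dressing effect.
- **Comparability.** With no randomisation described, nothing in the plan protects against arms that differ in fluid volume or case length. If they did differ, the unadjusted SEM comparison would carry that difference and it would be read as an effect of the dressing. The risk-factor analysis is exposed in the same way: an association of SEM-defined injury with surgery length could partly reflect fluid.

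**Working it through.** **No plan figure to reproduce.** The documents give no SD for the SEM Delta, no expected fluid shift, no error rate for the 0.6 pF cut-off, no expected incidence and no sample size. The cut-off is a definition. The argument therefore rests on the text, and the arithmetic below shows direction and sensitivity only.

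**Step 1: the text.**

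| Element | What is specified | Can it reveal or remove a fluid shift? |
|---|---|---|
| Measurement | Total tissue water | No |
| Classification | Same-site difference, 0.6 pF or more | No: no reference site, no common shift subtracted |
| Sites | Eight, all on the front of the body, all in prone patients | No: none is away from the dependent surface |
| Arm comparison | Fisher's exact test | No: takes no covariates |
| Further arm comparison | Cochran-Mantel-Haenszel | Unclear: strata not named |
| Regression | Surgical factors, controlling for group | Possibly: open list, fluid volume not named |

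**Step 2: false positives under an assumed shift.** Suppose there is no injury and the Delta is normal with mean m (the fluid shift) and standard deviation SD. One site is positive with probability p = 1 − Φ((0.6 − m)/SD). If any of four independent face sites counts (an assumption; the plan does not say how face sites are combined), the face is positive with probability 1 − (1 − p)^4. At SD 0.3 pF:

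- m = 0: p = 1 − Φ(2) = 0.0228; face 1 − 0.9772^4 = 8.8%
- m = 0.1: p = 1 − Φ(1.667) = 0.0478; face 1 − 0.9522^4 = 17.8%
- m = 0.3: p = 1 − Φ(1) = 0.1587; face 1 − 0.8413^4 = 49.9%

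A generalised process would make sites move together, so independence is the extreme case. With equal correlation ρ between the four sites, integrating over a shared normal component gives, at SD 0.3 pF:

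| ρ | m = 0 | m = 0.1 | m = 0.3 |
|---|---|---|---|
| 0 | 8.8% | 17.8% | 49.9% |
| 0.5 | 7.2% | 13.9% | 37.3% |
| 0.8 | 5.2% | 10.2% | 28.4% |
| 1 | 2.3% | 4.8% | 15.9% |

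Over SD 0.2 to 0.5 pF and ρ from 0 to 0.8, the 0.3 pF shift gives 13.6% (SD 0.2, ρ 0.8) to 72.3% (SD 0.5, ρ 0). For each pair of SD and ρ this exceeds the no-shift value. At SD 0.5 with independent sites, however, 38.7% of faces are positive with no shift at all, which is measurement noise and not fluid.

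**Step 3: dilution when both arms are affected equally.** With false-positive rate f in both arms, the observed rate is p + (1 − p)f, so the difference shrinks by the factor (1 − f). Assume true rates of 30% and 10%, with 62 per arm (the number that gives about 80% power at f = 0, two-sided 5%, normal approximation):

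| f | Observed rates | Difference | Power |
|---|---|---|---|
| 0 | 30% v 10% | 20 points | 80% |
| 0.1 | 37% v 19% | 18 points | 61% |
| 0.2 | 44% v 28% | 16 points | 46% |
| 0.3 | 51% v 37% | 14 points | 35% |

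**The case against.** The strongest reply is that a mechanism has been described but no effect shown. Nothing in the documents says that fluids or prone positioning move a 4 mm reading by 0.6 pF, and only swelling that reaches the cut-off would count. A reader might infer that generalised edema *is* being scored as pressure injury, or that any swollen face is a case. The documents do not support that; they support only that it can happen. This part of the reply stands.

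Four further points have weight.

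- The regression covers surgical factors and its list of factors is open, so fluid volume could already be in it; surgery length is named. It would be wrong to say that the plan rules out adjustment. But nothing commits to fluid volume, and the model is described as a risk-factor analysis, not as the comparison of arms.
- Visual IAPrI is a separate outcome that does not use SEM, and the SEM rule says only that the change is indicative of injury. That limits the reach of the point to one of the two outcomes.
- Comparisons on days 2 and 3 give some view of whether a transient swelling drives the result, though no persistence rule is stated.
- A reader might infer that the arms do differ in fluid volume or case length. The documents do not say so; an undescribed allocation is a lack of protection, not evidence of imbalance.

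It is also true that adjustment leaves every classification unchanged. Surgery length is a pressure exposure as well as a correlate of fluid, so the model cannot separate the two mechanisms. That does not disqualify it as a covariate: it remains a legitimate confounder of the arm comparison.

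**Conclusion.** The point holds in a limited form. By the protocol's own account of the device, a same-site SEM Delta of 0.6 pF or more cannot distinguish local pressure damage from a systemic or positional rise in tissue water. No reference site corrects for this, and the specified Fisher comparison is unadjusted although no randomisation is described and fluid volume is on file.

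The frequency of such false positives cannot be estimated from the documents. The percentages in the working rest wholly on an assumed SD, shift and between-site correlation, and should be read only as a range. The direction is firmer, given that the Delta is a post-operative rise: a positive shift without injury raises the SEM-based count. If that happens equally in both arms it dilutes a dressing effect; bias between arms would need fluid volume, case length or swelling to differ by arm. The visual outcome is untouched.

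**What to change.** 1. Beside the Fisher result, add a sensitivity analysis of the SEM outcome: logistic regression of SEM Delta at or above 0.6 pF on group, with intraoperative fluid volume and surgery length as covariates. Use a penalised or exact method if events are few. Specify it before it is run; the plan is written in the past tense, so if the SEM results are already known, label the analysis post hoc.
2. In the conclusions, describe a participant who is positive on SEM alone, with visually normal skin, as having *raised SEM*, not an acquired pressure injury.
3. Optionally, report by arm how many SEM-positive participants rise at many of the eight sites and how many at one or two. This is descriptive only: every site is pressure-exposed, so a multi-site rise could equally be widespread pressure.
4. State the sign of the SEM Delta.

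The cost is some plan wording and one extra model on data already abstracted. The adjusted estimate will be less precise, by an amount that cannot be stated without a sample size or event count, and the stated SEM-based incidence may fall. The model deals with confounding between arms; it does not repair misclassification, which is why the wording in item 2 is needed as well.
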